1. PROTOCOL SUMMARY

An Independent Review of Safety Data from a Closed Clinical Study Using Irrisept (Protocol # IRR-CT-901-2013-01)	
Study Type	Retrospective Review
Short Title	Retrospective Independent Safety Review of Closed Irrisept Study
Study Objective	The objective of this retrospective review is to ensure that all safety data from the closed study have been accurately identified, verified and independently adjudicated. The Sponsor will use the safety data from this review to complete a final study report and ensure the product risk assessment documentation is current and complete.
Study Design	Retrospective review of safety data previously collected in a closed randomized clinical trial (Protocol IRR-CT-901-2013-01) prospectively-conducted between 2013 and 2016.
Study Sites	17 sites who originally participated and enrolled subjects in the closed study
Study Population	625 subjects who were previously consented in the closed study. There is no new subject enrollment involved in this retrospective review. The study population, including inclusion and exclusion criteria, was previously defined in the closed study protocol.
Study Duration/ Follow-up	There is no subject follow-up involved in this retrospective review. The study duration and follow-up was previously defined in the closed study protocol.
Key Study Parameters	Preexisting safety data from the closed clinical study including all adverse events and any reports of device deficiencies.
Key Study Endpoint	As defined in the closed study Protocol IRR-CT-901-2013-01, this retrospective review will complete the safety endpoint analysis of adverse events associated with use of Irrisept as compared to use of the Standard of Care for irrigation.

2. BACKGROUND INFORMATION

2.1 Study Rationale

Between 2013 and 2016, an Irrimax-sponsored prospective clinical study entitled, “*A Phase IV, multicenter, prospective, randomized, controlled clinical study to compare the IrriSept system versus Standard of Care (SoC) on the prevalence of Surgical Site Infection (SSI) in patients with abdominal trauma or acute surgical abdomen*”, IRR-CT-901-2013-01, was conducted in the United States under IRB approval. A total of 19 sites were planned to participate in the study with only 17 sites enrolling subjects in the study, as listed above. A total of 625 subjects were consented and 600 subjects were randomized (1:1) and received irrigation either with Irrisept or the Standard of Care. Subjects were followed through study completion, and Protocol IRR-CT-901-2013-01 was previously closed with the IRBs. However, the Contract Research Organization and Sponsor’s executive management responsible

for undertaking this study during that period of time (2013-2016) were unable to complete the necessary monitoring activities and final data reporting.

In 2019, the Sponsor, under new management, intends to fulfill the Sponsor responsibilities by preparing a final study report for Protocol IRR-CT-901-2013-01. Upon recent review of the previously reported safety data from this closed study, the Sponsor determined that remonitoring of the subjects' source records is necessary to ensure complete and accurate reporting. Furthermore, an independent review of the device-related safety data by a Medical Monitor is needed.

Therefore, the Sponsor is initiating a retrospective review of the safety data, specifically all adverse events (AEs) and any device deficiencies that occurred in the closed clinical study based on the subjects' source records, including identifying any events or deficiencies that may not have been previously reported on case report forms (CRFs). The purpose of this retrospective review is to ensure all safety data on Irrisept are known and the product risk assessment documentation is current. All reported AEs will be assessed by an independent Medical Monitor. Device-related adverse events will be evaluated for any required reporting to regulatory authorities.

The Sponsor does not intend to repeat the prospective clinical study IRR-CT-901-2013-01 or obtain any new information that was not previously collected in the subjects' source records for the closed study. The Sponsor's intent is solely to ensure all safety data are reported accurately and completely. This retrospective review will not recover or remonitor the previously reported efficacy data.

The subjects who participated in the closed clinical study (IRR-CT-901-2013-01) have been consented and signed an informed consent form and authorization to use and disclose protected health information under the HIPAA Privacy Rule for that study. As a retrospective review of subjects' data previously collected under the closed study, there should be no need for any additional informed consent of the subjects for this review. This review poses no risks to the previously enrolled subjects, and the subjects' prior authorization to use and disclose protected health information remains in effect with only the Sponsor and the Contract Research Organization, working on behalf of the Sponsor, having access to review the subjects' medical records to verify the accuracy of the safety data as reported on the CRFs.

2.2 Product Description

In the closed clinical study (IRR-CT-901-2013-01), subjects were randomized to receive irrigation with Irrisept (study medical device) or with the Standard of Care, which was determined at the sole discretion of the Investigator or institution. Refer to the *U.S. Investigator's Brochure for Irrisept Wound Debridement and Cleansing System* for detailed product information and a report of prior investigations, including literature, pre-clinical and clinical studies.

Irrisept® Wound Debridement and Cleansing System is an irrigation device comprised of a bottle of 0.05% Chlorhexidine Gluconate (CHG) in 99.95% Sterile Water for Irrigation, USP and an applicator.

Irrisept is a wound cleansing delivery system with mechanical action that effectively loosens and removes wound debris. The CHG is a preservative to inhibit microbial growth in the solution.

Irrisept is a prescription device and a combination product intended for use by healthcare professionals. Irrisept received 510(k) clearance (K080779) from the U.S. Food and Drug Administration (FDA) and has been marketed in the U.S. since 2009.

This retrospective review is non-significant risk because the review involves only assessment of previously collected subject data. This retrospective review does not involve any subject participation or use of any product.

3. STUDY OBJECTIVE

The objective of this retrospective review is to ensure that all safety data from the closed Irrisept study have been accurately and completely identified, verified and independently adjudicated. The Sponsor will use the safety data from this review to complete a final study report and ensure the product risk assessment documentation is current and complete.

4. STUDY DESIGN

This is a retrospective review of existing safety data from a prospective randomized clinical trial, conducted between 2013 and 2016, which was closed without a final clinical study report being issued.

5. STUDY POPULATION AND FOLLOW-UP

The study population, including inclusion and exclusion criteria, was defined in the closed study Protocol IRR-CT-901-2013-01. The closed study protocol allowed for enrollment of up to 1,100 subjects. At the 17 sites who enrolled subjects in the closed study, 625 subjects were consented, 600 subjects were randomized and received irrigation with either Irrisept or the Standard of Care, and 450 subjects completed the study. The study duration and follow-up schedule were previously defined in the closed study protocol. The closed study involved two visits: Visit 1 included screening, peri-operative and post-surgical; and Visit 2 was 30 days post-procedure.

This retrospective review will include all 625 previously consented subjects from Protocol IRR-CT-901-2013-01. The review will assess for documentation of informed consent for these subjects, and the subjects' source medical records will be reviewed for potential adverse events. There is no new subject enrollment or follow-up as part of this retrospective review.

6. STUDY ENDPOINT

The closed study Protocol IRR-CT-901-2013-01 defined primary and secondary efficacy, exploratory and safety endpoints. The previously defined safety endpoint from this closed study was a clinical review and analysis of adverse events.

This retrospective review is intended to complete the safety endpoint analysis of adverse events associated with use of Irrisept or the Standard of Care for irrigation. Note that this review does not include an evaluation of the efficacy or exploratory endpoints, as defined in the closed study Protocol IRR-CT-901-2013-01.

7. STUDY DATA PARAMETERS

The study data parameters are limited to the preexisting safety data from the closed study. This retrospective review involves identification, verification and adjudication of all adverse events in the study for all enrolled subjects based on the source medical records. The adverse events will be summarized by group, type, severity and device-relatedness. In addition, as part of the safety data review of the closed study, any device deficiencies with Irrisept documented in the source records during the closed study when the study device was used will be identified, even if the deficiency was not associated with an adverse event. Any device deficiencies will be investigated to ensure the deficiency could not lead to an adverse event if the problem were to recur.

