7.2 Safety Data Reporting

7.2.1 *Safety Data Reporting Responsibilities*

The responsibilities for safety data reporting in this retrospective review are summarized below.

- **Investigator:** The Investigator is responsible for recording all previously identified and newly identified adverse events and device deficiencies on the CRFs. Investigators must record on the source document and eCRF their opinion concerning the AE severity, relationship of the AE to device, seriousness categorization per the event definitions, and whether any device effect is anticipated or unanticipated. The Investigator will follow all IRB/EC and institutional reporting requirements of AEs and SAEs, including for any new safety information or adverse events which may be identified retrospectively. Investigators are required to prepare and submit complete, accurate and timely reports on this clinical investigation to the Sponsor, IRB/EC and/or regulatory authorities, when necessary.
- **Contract Research Organization (CRO):** The CRO is responsible for source data review of AEs and device deficiencies. As needed for monitoring activities, the CRO is responsible for appropriate follow-up with the Investigator, Sponsor and independent Medical Monitor, as per the study's Medical Monitoring plan. The CRO is also responsible for data management of this retrospective review.
- **Medical Monitor:** Each AE will be assessed by an Independent Medical Monitor for severity, relatedness to the device, seriousness categorization per the event definitions, and whether any device effect is anticipated or unanticipated. A firewall will be established between the Sponsor and its CRO representatives, and the independent Medical Monitor to reduce bias in adjudication of AEs.
- **Sponsor:** The Sponsor will assess all adverse device effects determined to be related to Irrisept based on the independent adjudication of the Medical Monitor. The Sponsor will investigate any reported device deficiencies as part of the complaint handling process and to ensure the deficiency could not lead to an adverse event if the problem were to recur. The Sponsor is responsible for any required safety reporting to the FDA or other regulatory authorities, such as per 21 CFR 803 (Medical Device Reporting), as applicable.

7.2.2 *Specific Considerations for AE Reporting*

1. Abnormal Vital Signs and Laboratory Values

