 - Investigator's medical opinion of likely cause of the event and device relationship
 - Description of device use during closed study, including any problems with the device or actions taken with the device as a result of the adverse event
- For subjects who have a device deficiency related to Irrisept identified in the Source records:
 - Dates of report and verification Irrisept was used for irrigation in closed study
 - Description and nature of deficiency
 - Documentation of whether the deficiency was related to any adverse event
 - Investigator's opinion if the deficiency could result in an adverse event if it were to recur

The Investigator or designee is responsible for completing, in a timely manner, an eCRF for each subject and all eCRFs for previously reported or newly detected AEs and device deficiencies. The Investigator or designee is responsible for reviewing completed eCRFs to attest that all data entered are complete and accurate after the monitor finishes the source document verification process. The Investigator is responsible for reviewing and signing each eCRF to indicate the Investigator has thoroughly inspected data and certifies its completeness and accuracy.

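### The objective promises independent adjudication of all safety data, but device deficiencies have no stated route to the Medical Monitor unless they are linked to an adverse event

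*Protocol*

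**What the plan says.** Protocol section 3 sets the objective that "all safety data from the closed Irrisept study have been accurately and completely identified, verified and independently adjudicated". The Protocol Summary and SAP 1.1 say nearly the same.

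The Key Study Parameters in the Protocol Summary describe the material as "Preexisting safety data from the closed clinical study including all adverse events and any reports of device deficiencies". Protocol 2.1 gives the review the same two-part scope and adds that "an independent review of the device-related safety data by a Medical Monitor is needed".

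On who does what, Protocol 7.2.1 states that "Each AE will be assessed by an Independent Medical Monitor". For deficiencies it states that "The Sponsor will investigate any reported device deficiencies as part of the complaint handling process". Protocol section 7 gives the aim of that work: "Any device deficiencies will be investigated to ensure the deficiency could not lead to an adverse event if the problem were to recur".

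Protocol 9.1 also has the site record, for each Irrisept deficiency, whether it was related to an AE, and the Investigator's "opinion if the deficiency could result in an adverse event if it were to recur".

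**The concern.** The objective promises a property that the working sections set up for only one of the two kinds of safety data. The review exists because monitoring and final reporting of the closed study were left incomplete, and its results feed the final study report and the product risk assessment. A report that repeats the objective could claim independent adjudication of all safety data when deficiencies had none.

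Protocol section 7 expressly wants deficiencies captured even when no AE followed. Those are the ones for which no step leading to the Medical Monitor is described. The Sponsor, who makes the device, investigates them under an aim phrased as a result to be secured rather than a question to be answered.

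**Working it through.** No arithmetic applies. The documents state no figure on this point, so the check sets the sections side by side.

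1. **Are deficiencies safety data?** Yes. The objective sentence does not name them, but the Key Study Parameters and Protocol 2.1 include them. The safety data definitions in Protocol 7.1 and SAP 2.2.1 cover both AEs and deficiencies.

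2. **Which data are independently adjudicated?** Each working section names AEs only:
   - Protocol section 7 speaks of adjudication for AEs. Deficiencies are identified and investigated.
   - Protocol 7.2.1 gives the Medical Monitor each AE, and ties the firewall to bias in adjudicating AEs.
   - Protocol 7.2.3 gives the Medical Monitor a separate adjudication of all identified AEs.
   - Protocol 9.2 describes the Medical Monitoring Plan as covering review and adjudication of AEs.

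3. **What do deficiencies receive?** The Investigator records them and gives the two judgements listed in Protocol 9.1. The CRO reviews source data, and 100% source data verification applies (Protocol 7.2.1 and 9.2). The Sponsor then investigates. Source review and verification test whether records are complete and accurate. They do not judge potential for harm.

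4. **Is there another route to the Medical Monitor?** Yes, for a deficiency linked to an AE. Adverse device effects include events from malfunction, inadequate instructions and use error (Protocol 7.1.3). Problems with the device are collected for subjects with an AE (Protocol 9.1), and the Medical Monitor rates each AE for device-relatedness. The ratings listed in Protocol 7.2.1 are severity, relatedness, seriousness and whether a device effect was anticipated. None asks about harm on recurrence. For a deficiency with no AE, no route is stated.

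5. **How is the recurrence question put?** The Investigator is asked neutrally whether the deficiency could cause an AE. The Sponsor's task is to ensure that it could not. The protocol thus already holds a neutral form but does not use it for the Sponsor.

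6. **What is reported?** SAP 3.5 promises a summary by type with other relevant information, plus individual data. TDA01 and LPD01 are named by title only. Nothing commits them to show either party's judgement, and neither document says what happens if Investigator and Sponsor disagree.

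**The case against.** The best reply is that the working sections agree with one another and only the objective is loosely worded. Protocol section 7 treats AEs and deficiencies separately. The endpoint in Protocol section 6 and SAP 2.2 is AEs alone. The call in Protocol 2.1 for independent review of device-related data is followed in the next paragraph by a statement that the Medical Monitor assesses AEs. The word *ensure* can be read as a duty to follow a problem through, since Protocol 7.2.1 places it within complaint handling and beside the Sponsor's regulatory reporting duties. SAP 3.5 leaves room to report the Investigator's opinion. The Medical Monitoring Plan is not among the documents, and Protocol 7.2.1 routes CRO follow-up with the Medical Monitor through it just after naming both AEs and deficiencies.

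Much of this stands. It shows that narrowing the objective would be enough to remove the inconsistency, and that some Medical Monitor involvement with deficiencies cannot be ruled out. It does not remove the mismatch: the objective says all safety data, and no section assigns independent adjudication of deficiencies.

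A reader might go further and infer that the Sponsor alone judges deficiencies, or that none is seen by anyone outside the Sponsor. The documents do not support that. The Investigator gives an opinion on the same recurrence question, and deficiencies linked to an AE reach the Medical Monitor through that AE. Nor do the documents show that the wording of the aim settles the Sponsor's conclusion in advance.

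**Conclusion.** The point holds as a mismatch between the stated objective and the assigned tasks. Deficiencies receive an Investigator opinion and a Sponsor investigation. They receive no Medical Monitor rating in their own right, and the two opinions have no stated rule for disagreement. The gap is widest for deficiencies without a linked AE. For those with one, only the recurrence question goes unrated by the Medical Monitor.

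No rate or count can be attached, because the documents give none. The consequence is for what the final report and risk assessment may properly claim about deficiencies.

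Two assumptions carry the conclusion: that safety data means the same in the objective as in Protocol sections 1 and 2.1, and that the Medical Monitoring Plan keeps to the scope given in Protocol 9.2. The text should be corrected before the report is written.

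**What to change.** - In Protocol 7 and 7.2.1, restate the aim of the Sponsor's investigation as *to determine whether the deficiency led to, or could on recurrence lead to, an adverse event*.
- In Protocol 7.2.1 and 9.2, add one Medical Monitor item per deficiency: could it lead to an AE (yes / no / cannot be determined).
- In SAP 3.5, TDA01 and LPD01, show the Investigator, Medical Monitor and Sponsor determinations side by side, so that any disagreement is visible in the report.
- If the Medical Monitor item is not added, limit the independent adjudication claim in Protocol sections 1 and 3 and SAP 1.1 to AEs.

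The cost is a wording change in both documents, a few extra ratings from a Medical Monitor already provided for, and added columns in one table and one listing. The Investigator's opinion is already collected. The downside is that more deficiencies may be reported as potentially harmful. The fallback costs only the wording of the objective.

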7.1 Safety Data Definitions

All adverse events and device deficiencies as defined below will be recorded and verified based on the source documents from the closed clinical study. The closed study (Protocol IRR-CT-901-2013-01) defined adverse events based on a combination of references (i.e., International Conference on Harmonisation (ICH) Guideline for Good Clinical Practice (GCP) (1996), International Organization for Standardization (ISO) 14155:2011 standard, and 21 CFR Part 812). For this retrospective review, the adverse event definitions are consistent with the closed study protocol; however, a few clarifications based on the ISO 14155:2011 standard have been described within these definitions.

7.1.1 Adverse Event

As defined in Protocol IRR-CT-901-2013-01, an **Adverse Event (AE)** is any untoward medical occurrence in a subject or clinical investigation which does not necessarily have a causal relationship with the medical device under investigation.

As described in ISO 14155, an adverse event includes:

- events that are related or not related to the study device (Irrisept), comparator (Standard of Care), or a study procedure; or
- events in users or other persons that are related to the study medical device (Irrisept).

Adverse events are categorized as serious or non-serious. A non-serious adverse event is any event that does not meet the definition of serious adverse event, as listed below.

7.1.2 *Serious Adverse Event*

As defined in Protocol IRR-CT-901-2013-01, a **Serious Adverse Event (SAE)** is an adverse event that results in one of the following outcomes: requires hospitalization; prolongs hospitalization; is life-threatening; results in congenital anomaly/birth defect; or results in death.

Furthermore, as described in ISO 14155, a serious adverse event includes any adverse event that has led to a serious deterioration in health that resulted in:

- In-patient hospitalization or prolongation of existing hospitalization;
 - This criterion applies if the event requires in-patient hospitalization with an overnight stay in hospital or, if in the opinion of the Investigator, prolongs an existing hospitalization.
 - Hospitalizations for less than 24 hours with no admission are not considered "hospitalization".
 - A planned hospitalization for a pre-existing condition (including for an elective procedure or routinely scheduled treatment) or a procedure required as part of the clinical study which has not worsened does not constitute an SAE.
- Permanent impairment in body structure or function;
- Medical or surgical intervention to prevent life-threatening illness or injury or permanent impairment of a body structure or function;
- Is life-threatening;
- Results in congenital anomaly/birth defect; or
- Results in death.

7.1.3 *Adverse Device Effect*

As defined in Protocol IRR-CT-901-2013-01, an **Adverse Device Effect (ADE)** is an adverse event that results from the presence or performance of the device or any component of the system.

As described in ISO 14155, an adverse device effect includes any event resulting from:

- Deployment, implantation or operation of the device
- Malfunction of the device
- Insufficient or inadequate instructions for use
- Use error or intentional misuse of the device

7.1.4 *Serious Adverse Device Effect*

As defined in Protocol IRR-CT-901-2013-01, a **Serious Adverse Device Effect (SADE)** is an adverse event related to the presence or performance of the device or any component of the system that results in one of the following outcomes: requires hospitalization; prolongs hospitalization; is life-threatening; results in congenital anomaly/birth defect; or results in death. The same ISO 14155 clarifications as documented above for SAE also apply to SADE.

7.1.5 *Unanticipated Serious Adverse Device Effect*

As defined in Protocol IRR-CT-901-2013-01, a **Unanticipated Serious Adverse Device Effect (USADE)** or **Serious Unexpected Device Effect** is any serious adverse effect on health or safety or any life-threatening problem or death caused by, or associated with, a device, if that effect, problem, or death was not previously identified in nature, severity, or degree of incidence in the investigational plan or application, or any other unanticipated serious problem associated with a device that related to the rights, safety, or welfare of subject.

As described in ISO 14155, an unanticipated serious adverse device effect is an effect by which its nature, incidence, severity or outcome has not been identified in the risk analysis report, as documented in the following section.

7.1.7 *Anticipated Adverse Device Effects Associated with Use of Irrisept*

Table 1 lists the potential risks associated with use of Irrisept based on the product risk analysis and the potential adverse device effects that are anticipated with these risks. Potentially serious adverse device effects (anticipated SADE) have been assessed as a lower probability of occurrence.

TABLE 1: POTENTIAL RISKS AND ANTICIPATED ADVERSE DEVICE EFFECTS FOR IRRISEPT		
Potential Risk	Risk Assessment and Risk Mitigations	Potential Anticipated Effects
Allergic or anaphylactic response to CHG	
Potential for allergic reaction
 
 Potential allergy to CHG is known to occur with other products containing CHG. However, serious allergic reaction is rare based on data published by the U.S. FDA on topical skin products containing CHG.¹ Product is labeled as do not use in patients with CHG allergy. A known CHG allergy was an exclusion criterion in the closed study protocol. 	
 ADE: Minor non-serious allergic reaction (e.g., rash, dermatitis, itching, rhinitis) SADE: Serious or life-threatening allergic reaction requiring medical intervention (e.g., shortness of breath, tachycardia, tightness in throat, dizziness, anaphylactic reaction)

¹ U.S. Food and Drug Administration website, “FDA Drug Safety Communication: FDA warns about rare but serious allergic reactions with the skin antiseptic chlorhexidine gluconate”; accessed September 2, 2016 at <https://www.fda.gov/drugs/drug-safety-and-availability/fda-drug-safety-communication-fda-warns-about-rare-serious-allergic-reactions-skin-antiseptic>

TABLE 1: POTENTIAL RISKS AND ANTICIPATED ADVERSE DEVICE EFFECTS FOR IRRISEPT		
Potential Risk	Risk Assessment and Risk Mitigations	Potential Anticipated Effects
Exposure to bio-incompatible material or chemical with potential for adverse tissue reaction	
Potential for toxicity reaction
 
 Patient contact materials have passed biocompatibility testing per ISO standard 10993-1. Manufacturing process validations and quality control procedures have been completed to ensure product integrity and quality. 	
 - ADE: Minor tissue irritation, as manifested by symptoms such as pain, erythema, edema, itching, burning - SADE: Severe adverse tissue reaction that requires or prolongs hospitalization, or requires medical or surgical intervention to prevent permanent impairment
Exposure to non-sterile or contaminated product	
Potential for infection
 
 Product is aseptically-filled and bottle and applicator surfaces are terminally sterilized. Sterilization, packaging and manufacturing process validations have been completed to ensure product integrity and sterility. Product contains CHG, which acts as a preservative to inhibit microbial growth in the solution, and the product has been tested to show preservative effectiveness. Bottle and applicator are sequentially double wrapped with CSR wrap serving as a microbial barrier. Product has been tested to show stability and sterility are maintained over the labeled shelf life. Surgical patients routinely receive antibiotics as part of the pre-op and post-op surgical care regimen since surgical site infection is a known complication of any surgery type. 	
 - ADE: Minor surgical site infection, wound infection or abscess, as manifested by symptoms such as erythema, edema, pus, fever, chills, pain - SADE: Severe infection that requires or prolongs hospitalization, or requires medical or surgical intervention to prevent permanent impairment

TABLE 1: POTENTIAL RISKS AND ANTICIPATED ADVERSE DEVICE EFFECTS FOR IRRISEPT		
Potential Risk	Risk Assessment and Risk Mitigations	Potential Anticipated Effects
Use of product for irrigation affects wound healing	
Potential for delay in wound healing
 
 Patient contact materials have passed biocompatibility testing per ISO standard 10993-1. Manufacturing process controls ensure product is not contaminated with any particulates from manufacturing. 	
 - ADE: Minor wound dehiscence, non-healing wound, granuloma or adhesion - SADE: Severe wound dehiscence or non-healing wound that requires or prolongs hospitalization, or requires medical or surgical intervention to prevent permanent impairment
Ineffective use of product with inability to remove wound debris	
Potential for ineffective irrigation or incomplete irrigation
 
 Surgeon routinely visually assesses surgical wound bed for effective debridement and clearance of particulates and wound debris. Saline is routinely available for surgical irrigation in the event that the Irrisept bottle cannot be used. 	
 - ADE: Minor non-healing wound, granuloma, adhesion, adverse tissue reaction or infection - SADE: Severe non-healing wound, granuloma, adhesion, adverse tissue reaction or infection that requires or prolongs hospitalization, or requires medical or surgical intervention to prevent permanent impairment
Incompatibility with other therapies used during the procedure	
Potential for incompatibility with other therapies (e.g., concomitant medications, other therapies used during surgery)
 
 No known incompatible medications or therapies with Irrisept. Irrisept is used an irrigation solution with short term exposure to the wound and surrounding tissues and is not ingested or injected. 	
 - ADE: Minor adverse tissue reaction - SADE: Severe adverse tissue reaction that requires or prolongs hospitalization, or requires medical or surgical intervention to prevent permanent impairment

